9.7 Individual Dose Limiting Toxicity

- Any single grade 3 AE or Lab abnormality
- Fecal occult blood remains positive for 3 consecutive stool samples, hemorrhoids are excluded
- Evidence of frank hematemesis or hematochezia/melena of any duration
- Any clinical signs or symptoms the PI has determined is unsafe to administer IP

If an individual subject in a cohort reaches dose limit toxicity as determined by any of the above criteria, the subject will not receive any additional doses, and will be withdrawn from the study. All subjects withdrawn from the study will undergo routine follow up safety monitoring.

9.8 Safety Oversight (Safety Review Committee, Independent Safety Monitor plus Safety Monitoring Committee)

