9.1.3 Electrocardiograms

A 12-lead ECG will be performed at approximately the same time each day. Subjects will be placed in a supine position for at least 10 minutes prior to recording an ECG. Triplicate 12-lead ECGs will be collected at the pre-dose on Day 1 (baseline) and a single ECG will be collected at other scheduled times. The screening and Day 1 ECG will be used by the PI to determine subject's eligibility for enrollment. The Day 1 ECG will be reviewed to determine if subjects are safe and appropriate to dose and will be used to determine baseline for waveform and QTc.

All ECGs will be reviewed by the PI or designee. ECGs with the following readings will be considered acceptable for study and will not be considered abnormal for study purposes unless the PI or physician designee believes they represent a new medical condition when compared to baseline ECGs. In such cases an AE will be documented and the subject will be

followed for safety evaluations as appropriate. The following pre-existing conditions identified at enrollment will not be considered adverse events:

- sinus bradycardia;
- sinus arrhythmia;
- early repolarization;
- nonspecific ST-T wave pattern or changes, mild or moderate right axis deviation;
- first degree AV block (PR interval less than 210ms is acceptable);
- nonspecific intraventricular conduction delay (QRS, or average of triplicate QRS; less than 120ms is acceptable);
- short PR interval (where no delta wave), and indeterminate axis.

The Sponsor may review all or individual screening or Day -1 ECGs or may delegate to determine if meets intention of entry criteria goal of enrolling healthy normal study subjects.

Three ECG tracings are made pre-dose. At least 2 of the 3 tracings should be acceptable/normal per (correct) machine reading and all three must be consistent with otherwise healthy normal individuals.

If a post-dose ECG demonstrates a prolonged QTc interval (>500 ms) or an increase of at least 60ms from baseline average, 2 more tracings should be captured within 10 minutes. The averaged QTc value of these 3 will be used for decision making relative to the halting rules described in [Section 9.6](#).

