In the event of a prolongation of QTc post dosing, the site will start telemetry monitoring of the subject and capture triplicate 12 lead ECG (3 tracings within a 5 minute period) every 30 minutes until the average for the triplicates has returned within 60ms of the baseline value at which time telemetry maybe discontinued. Persistent (1 hour or more) elevation in QTc (>500 ms) should prompt immediate consideration of transfer to appropriate emergency department for further evaluation, monitoring, and/or treatment.

In the event of a change in ECG wave forms consistent with a change in cardiac function or conduction when compared to baseline tracings, or in the event of a subject with possible cardiac related symptoms, repeat ECG should be obtained every 30 minutes until wave form change reverts to baseline appearance, or symptoms resolve, or are determined not to be cardiac in origin. Subjects with cardiac related symptoms associated with ECG changes will be transferred to appropriate emergency department for further evaluation and treatment.

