9.6 Study Halting Criteria

General:

- Any SAE
- Three or more subjects within a cohort, with the same Grade 2 event ;
- Any single Grade 3 or above finding (with the exception of aPTT as explained below);
- Evidence of hematemesis or hematochezia in 2 or more subjects
- Any other findings that, at the discretion of the PI, indicate that the study should be halted;

Electrocardiograph (ECG):

Two or more subjects within a cohort who meet any of the criteria below:

- PR: >220 ms
- QRS: >120 ms
- QTcF > 450 ms for men and >470 ms for women; or
- Change from baseline (average of pre-dose triplicate ECGs): QTcF >60 ms.

Decisions are to be based on an average QTcF value of triplicate ECGs. If an ECG demonstrates a prolonged QT interval, 2 more ECGs should be obtained over a 10 minute period. The averaged QTcF values of the 3 ECGs will then be used for decision making.

Laboratory criteria:

- Two or more subjects within a cohort have a Grade 3 increase in aPTT (confirmed on repeat) as defined by the FDA toxicity grading scale as modified for this study and as appropriate for the administration of UV-4B ([Appendix II](#)).

If any of the above events occur, the study will be halted and the SMC will review the available safety data to determine if the study should proceed as planned. If none of the events described above have been observed, dose escalation will proceed according to the protocol requirements.

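### One asymptomatic subject with a confirmed QTcF above 500 ms, or more than 60 ms above baseline, meets no numeric stopping rule

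*Protocol*

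**What the plan says.** Three parts of the protocol bear on one subject's QTc.

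- **Section 9.1.3 (Electrocardiograms).** A post-dose QTc above 500 ms, or a rise of at least 60 ms over the baseline average, calls for two further tracings. "The averaged QTc value of these 3 will be used for decision making relative to the halting rules described in" Section 9.6. The site starts telemetry and takes triplicate ECGs every 30 minutes "until the average for the triplicates has returned within 60ms of the baseline value at which time telemetry maybe discontinued". A QTc above 500 ms lasting an hour or more should lead the site to consider transfer. Transfer is mandatory in one situation: "Subjects with cardiac related symptoms associated with ECG changes will be transferred to appropriate emergency department".
- **Section 9.6 (Study Halting Criteria).** The ECG limits are PR >220 ms, QRS >120 ms, QTcF >450 ms (men) or >470 ms (women), and a QTcF change >60 ms. All sit under one condition: "Two or more subjects within a cohort who meet any of the criteria below".
- **Section 9.7 (Individual Dose Limiting Toxicity).** A subject stops dosing and is withdrawn for "Any single grade 3 AE or Lab abnormality", for fecal occult blood positive in three successive stools, for "Evidence of frank hematemesis or hematochezia/melena of any duration", or when the PI judges further dosing unsafe. No item concerns the ECG.

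**The concern.** Section 9.1.3 directs the confirmed value to a rule that one subject cannot trigger, and the section governing individual subjects does not mention it. Section 9.1.3 says when telemetry may end but not whether the next 8-hourly dose is given.

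The protocol handles its other two-subject signals differently. Section 9.6 halts the study if "Two or more subjects within a cohort have a Grade 3 increase in aPTT (confirmed on repeat") and for "Evidence of hematemesis or hematochezia in 2 or more subjects". Each has a single-subject stop in 9.7. The ECG rule does not.

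At stake is whether a healthy volunteer with marked, confirmed QTc prolongation receives the next dose. With up to two sites, the same value could be handled differently at each. No analysis in the SAP is affected.

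**Working it through.** The documents state no operating figure for the ECG rule, so there is none to reproduce. The check follows each route by which one subject's QTcF could stop dosing, then counts the doses exposed.

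**Routes for a subject with no cardiac symptoms who is not transferred**

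1. *9.1.3 to 9.6.* The cohort has 8 subjects. One is affected, so at least 1 of the other 8 − 1 = 7 must also meet a PR, QRS or QTcF limit. One subject at any QTcF value does not halt the study under the ECG rule.
2. *9.7 by name.* There is no ECG item. Withdrawal reason 6 in Section 5.3.3 refers to the halting criteria but cross-references 9.7. Reading it as 9.6 brings back the two-subject condition.
3. *9.6 or 9.7 by grade.* Appendix II has no QTc row. Section 9.2.1 records findings outside the grading criteria as Grade 0. If the general clinical-AE row is used, an event that does not interfere with activity is Grade 1; Grade 3 needs both prevented activity and medical intervention. Neither result reaches Grade 3.
4. *SAE.* Section 9.2.2 would pause dosing if the PI or Sponsor called the finding an important medical event. That is a judgement.
5. *PI clauses in 9.6 and 9.7, and SMC consultation* (Protocol Summary and Section 9.8.2). These are also judgements.

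Outside this case a rule does apply: cardiac symptoms with ECG changes require transfer, an emergency room visit is Grade 4 in Appendix II, and Grade 3 or above halts the study under 9.6.

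**Two-subject rules compared**

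| Signal in 9.6 | Single-subject counterpart in 9.7 |
|---|---|
| Grade 3 aPTT | Yes: any single Grade 3 laboratory abnormality |
| Hematemesis or hematochezia | Yes: frank bleeding of any duration |
| ECG intervals | None |

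**Doses remaining**

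Total doses: 3 per day × 7 days = 21. Section 7.3.2 places the daily ECG after the morning dose, so by the ECG on Day *d*, 3(*d* − 1) + 1 doses have been given and 20 − 3(*d* − 1) remain.

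| Day of scheduled ECG | 2 | 3 | 4 | 5 | 6 | 7 |
|---|---|---|---|---|---|---|
| Doses remaining | 17 | 14 | 11 | 8 | 5 | 2 |

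These counts apply to scheduled ECGs. A 12-lead prompted by telemetry after the first dose on Day 1 would leave 21 − 1 = 20.

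**Why both limits are needed**

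- Baseline 441 ms, post-dose 501 ms: 501 − 441 = 60 ms, which is not >60. Only the absolute limit catches it, and likewise for any higher baseline.
- Baseline 400 ms, post-dose 461 ms: 461 − 400 = 61 ms, which is >60 but below 500 ms. Only the change limit catches it.

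**The case against.** The strongest reply is that this is a resident, closely watched volunteer. The PI or designee reads every ECG, QTc prolongation brings telemetry and half-hourly triplicates, and 9.7 lets the PI stop dosing. Once doses are missed, Section 7.3.2 sends continued participation to the PI with the sponsor and NIAID medical monitors. A competent investigator may well stop. All of this stands, and it is why the point is modest. But each safeguard is discretionary, and the 7.3.2 review begins only after a dose has been missed.

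The Amendment 1 log says 9.6 and 9.7 were revised to match FDA recommendations, so the omission might be deliberate. The log does not show that an individual ECG limit was considered and rejected.

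Safety pharmacology, clinical safety and potential risks are redacted, so a rationale could sit there. That limits what can be said about QTc risk, but background text would not replace a line in 9.7.

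Finally, a 9.7 entry means withdrawal, whereas the missing instruction is about the next dose; it also leaves PR and QRS without an individual limit. Both observations are correct. Section 7.3.2 tolerates up to four missed doses after steady state, so a hold would be workable, but nothing orders one. Withdrawal is how the protocol treats its other individual limits, and QTc is the interval for which 9.1.3 already defines a trigger and confirmation.

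**Conclusion.** The concern holds. For an asymptomatic subject who is not transferred, a confirmed QTcF >500 ms or a rise >60 ms meets no numeric individual stopping rule. This is a gap in the written rule, not a contradiction. Of the three two-subject rules in 9.6, two have a single-subject counterpart in 9.7 and the ECG rule has none.

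If nobody acted, up to 17 of 21 doses could follow a scheduled ECG, or 20 after an unscheduled Day 1 tracing. Neither is an expected exposure. The 17 assumes that the Day 2 ECG follows the morning dose; taken before it, 18 would remain. The frequency of such a case cannot be estimated from the visible documents, and nothing in them shows that UV-4B prolongs QTc. The conclusion rests on the unredacted text. It is a cheap safety improvement.

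**What to change.** Add one item to Section 9.7: *Confirmed triplicate-mean QTcF >500 ms, or an increase >60 ms from the Day 1 pre-dose triplicate average.* Leave the two-subject rule in 9.6 and Appendix II unchanged. The thresholds, triplicate confirmation and baseline are already in 9.1.3 and 9.6, and SAP Section 10.7.6 already tabulates both categories, so no new procedure is needed. An amendment is already foreseen for Cohorts 4 and 5; making the change earlier would also cover Cohorts 1 to 3.

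The cost is that an occasional subject is withdrawn by rule instead of by PI judgement, and Section 5.3.3 allows no replacement after randomization. The cohort then falls from 6 to 5 active subjects or from 2 to 1 on placebo. If the QTc change is unrelated to drug, the chance that the subject is on placebo is 2/8 = 25%. Losing one active subject leaves at most 6 − 1 = 5 Day 7 values at that dose, still above the SAP Section 10.6.3 minimum of 3 per dose for the power model if the others are evaluable.

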3.2 Study Outcome Measures

3.2.1 Primary Outcome Measures

- Evaluation and occurrence of AEs and serious adverse events (SAEs)
- Determination of changes from baseline for clinical laboratory tests

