5.3.3 Reasons for Withdrawal

Subjects will be informed that they have the right to withdraw from the study at any time for any reason without prejudice to their medical care. Data collected for withdrawn subjects will be evaluated for safety and PK.

Subjects may be withdrawn from the study for any of the following reasons:

1. Withdraws consent;
2. Noncompliance with study procedures and/or requirements;
3. Death;
4. Pregnancy;
5. In the opinion of the site PI and Sponsor, does not meet eligibility criteria upon admission to unit;
6. Has met Halting Criteria (see [Section 9.7](#))
7. Administrative reasons/other.

In all cases of withdrawal, the reason for withdrawal will be recorded. Subjects who are withdrawn from the study will be asked to complete all Day 15 ± 1 safety assessments including follow-up of any AEs prior to termination from the study. Once randomized, subjects who withdraw from the study for any reason will not be replaced.

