7.5 Early Termination Visit

The clinic will make every effort to perform all assessments outlined for the follow-up visit (Day 15±1) if a subject is terminated prematurely from the study. All information collected will be documented in the subjects study records including eCRF.

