11.4.3 Procedures for Handling Missing, Unused, and Spurious Data

All available scheduled visit data will be included in data listings and tabulations. In addition, unscheduled visit data will be included in data listings. No imputation of missing values will be performed. Percentages of subjects with AEs or laboratory toxicities will be based on non-missing values. Data that are potentially spurious or erroneous will be examined under the auspices of standard data management operating procedures.

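### A subject with a dose-limiting toxicity is withdrawn from the study as well as from dosing, so the fixed-day safety series after the toxicity is no longer assured

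*Protocol*

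**What the plan says.** Protocol Section 9.7 lists the individual DLT criteria and gives one joint consequence: "the subject will not receive any additional doses, and will be withdrawn from the study". The next sentence adds: "All subjects withdrawn from the study will undergo routine follow up safety monitoring". It names no visits, days or tests.

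Two other sections say what a withdrawn subject is asked to do. Section 5.3.3: "Subjects who are withdrawn from the study will be asked to complete all Day 15 ± 1 safety assessments including follow-up of any AEs". This is to happen before termination, without saying whether that means at removal or on Day 15. Section 7.5 promises best efforts at the same set "if a subject is terminated prematurely from the study". As described in Section 7.4, the set includes a full laboratory panel, an ECG, vital signs and a physical examination. Section 8.2.1 has a parallel rule: three consecutive positive fecal occult blood samples lead to GI referral and withdrawal from the study. Randomized subjects who withdraw are not replaced (5.3.3).

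On the analysis side, Section 3.2.1 makes this a primary outcome: "Determination of changes from baseline for clinical laboratory tests". Section 11.4.3 says "No imputation of missing values will be performed", and SAP Section 10.1 agrees. Section 11.4.3 puts scheduled-visit data into both listings and tabulations, but mentions only listings for unscheduled visits. Section 7.6 also sends unscheduled data to listings.

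**The concern.** Stopping product and leaving the study are different events. Section 9.7 makes the first trigger the second, and it does so for subjects selected by toxicity. Once withdrawn, they have no stated place in the daily in-clinic assessments or the Day 10 visit.

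Laboratory change from baseline is summarized by treatment over the duration of the study. If a DLT subject contributes nothing on later scheduled days and nothing is imputed, those days describe only the subjects who stayed on the dose. The fixed-day off-product course, across all parameters and not just the abnormal one, is also evidence that the Safety Monitoring Committee (SMC) and FDA would want when they review a cohort of six active subjects.

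**Working it through.** **Step 1. Reproduce the plan's count.** Protocol Table 6 gives 11 full samples each for chemistry, hematology and coagulation. From Section 8.2.1 and Appendix IV: screening 1 + Day -1 1 + Days 2–8 7 + Day 10 1 + Day 15 1 = 11, which agrees. The post-dose full panels are 7 + 1 + 1 = 9. ECGs and vital signs are also scheduled on those nine days.

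**Step 2. Scheduled days without a commitment.** For a DLT on Day d, days left = number of days in {2, 3, 4, 5, 6, 7, 8, 10, 15} later than d. The withdrawal text names one set, so days without a commitment = days left − 1.

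| DLT on Day | Days left | Named set | No commitment |
|---|---|---|---|
| 1 | 9 | 1 | 8 |
| 2 | 8 | 1 | 7 |
| 3 | 7 | 1 | 6 |
| 4 | 6 | 1 | 5 |
| 5 | 5 | 1 | 4 |
| 6 | 4 | 1 | 3 |
| 7 | 3 | 1 | 2 |

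This credits the named set to one of the remaining days. If it is done at removal instead, the last column rises by 1.

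**Step 3. Share of the dose group.** Each cohort has 6 active subjects and no replacement, so one DLT is 1/6 = 16.7%.

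**Step 4. How often.** The documents give no DLT rate. Assuming a probability p per active subject, the chance of at least one DLT among six is 1 − (1 − p)^6: 26.5% at p = 5%, 46.9% at 10%, 73.8% at 20%, 88.2% at 30%. These cover all DLTs; those that do not halt the study are a subset.

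**Step 5. DLT criteria (9.7) against halting criteria (9.6).**

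| DLT | Halts the study by itself? |
|---|---|
| Grade 3 event or laboratory value other than aPTT | Yes |
| Single Grade 3 aPTT | No; two or more subjects in a cohort, confirmed on repeat |
| Fecal occult blood positive in three consecutive samples | No |
| Frank bleeding (hematemesis, hematochezia or melena) in one subject | No, unless Grade 3 or higher or an SAE; the bleeding rule needs two or more subjects |
| Investigator judges further dosing unsafe | Not automatically; the investigator has discretion to halt |

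Where the answer is yes, SAP Section 6 stops dosing for everyone under treatment but continues safety evaluation. It does not say whether a subject withdrawn under 9.7 is included. Where the answer is no, that sentence does not apply.

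**Step 6. Where later values go.** Repeat laboratory tests prompted by an adverse event (9.2.3) and taken at unscheduled visits fall under Sections 7.6 and 11.4.3: listings. The SAP makes no contrary provision for later-day laboratory summaries. For ECGs it is partly different: the outlier analysis in SAP Section 10.7.6 includes unscheduled readings.

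**The case against.** A reader might infer that safety data on a DLT subject end with one panel. The documents do not support that. Section 9.7 promises follow-up monitoring, adverse events are followed to resolution or stability (9.1.1), and Section 9.2.3 provides for repeat laboratory tests and ECGs as appropriate. QTc prolongation and positive fecal occult blood have their own repeat rules (9.1.3, 8.2.1). The abnormality that caused the DLT would be followed. What remains unassured is the fixed-day series, including parameters unrelated to the event.

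A reader might also picture a Grade 3 ALT rise in one subject while the other five continue to a reassuring Day 8 mean. Under Section 9.6 that finding halts the study, and SAP Section 6 keeps safety evaluation going, so the example fails.

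Nor do the documents show that escalation would be misled. DLTs are listed individually, events leading to discontinuation are summarized (SAP 10.7.2), and shift tables and Grade 1 or higher summaries are produced (SAP 10.7.4). Summaries show n, there is no inferential safety analysis, and SMC and FDA review precede each escalation. With six active subjects, a DLT would be seen.

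Finally, the point gives no ground for extra PK samples. The Day 7 profile is lost because the final dose is not given, later samples would be off-drug concentrations, and the PK population requires complete scheduled post-dose measurements (SAP Section 9).

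All of this stands and narrows the point. None of it commits the site to the remaining scheduled days or brings unscheduled results into the later-day laboratory summaries.

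**Conclusion.** The point holds in a limited form. Section 9.7 ties the end of dosing to the end of study participation, and the only assessments named afterwards are one Day 15-type set. Between 2 and 8 scheduled post-dose assessment days have no commitment, depending on the day of the DLT; the figure is 6 of 9 for Day 3. Later-day summaries of a primary outcome can therefore omit subjects because of toxicity, at 1 in 6 active subjects per DLT. The counts assume that the undefined monitoring in 9.7 is not read as the full schedule; a site that read it that way would collect the data.

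The gap is widest for DLTs that do not halt the study by themselves. For those that do, the issue is reconciling 9.7 with SAP Section 6. The effect is on the completeness of descriptive summaries and of the off-product course. It does not amount to loss of all later safety data or a demonstrated bias in escalation. It is worth correcting because the correction is cheap.

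**What to change.** Leave the DLT criteria and the dosing consequence as they are.

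- **Protocol 9.7, with matching wording in 5.3.3, 7.5 and the withdrawal sentence in 8.2.1:** distinguish discontinuation of study product from withdrawal from the study. State that, unless consent is withdrawn, a discontinued subject remains on the already scheduled safety assessments (laboratory tests, ECG, vital signs, examinations) through Day 15. Leave the GI referral in 8.2.1 untouched.
- **Reconciliation:** align 9.7 with the statement in SAP Section 6 that safety evaluation continues after a halt. Correct item 6 of 5.3.3, which refers to halting criteria but points to 9.7, the DLT section.
- **SAP 10.7:** keep these values in the by-treatment safety summaries with an off-product flag.

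No new type of assessment is needed. The costs are a protocol amendment with IRB review, extra days or visits for some off-drug subjects, and one programmed flag.
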